6.2.4. Feasibility of obtaining self-swabs

6.2.4.1. Percentage of participants administering the self-swab at self-swab #1 and self-swab #2

- a. Number of participants who administered self-swab #1 divided by total number of participants in the study, reported as a percentage.
- b. Number of participants who administered self-swab #2 divided by total number of participants in the study, reported as a percentage.
- c. Number of participants who administered self-swab #1 and self-swab #2 divided by total number of participants in the study, reported as a percentage.

The analysis set for this analysis will be the FAS (as described in [Section 4](#)), excluding those participants who experienced technical issues due to study operational errors (e.g., received the wrong instructions for self-swabs).

6.2.4.2. Percentage of participants reporting symptoms in the Electronic diary, who have a self-swab collected at or around symptom onset

- a. Number of days from symptom onset (reporting new or increased symptoms in the Electronic diary) to Record Swab #2 day in the Electronic diary averaged across participants who administered self-swab #2. Compute mean, SD, median, maximum and minimum days across participants.
- b. Number of participants who administered self-swab #2 and reported new or increased symptoms in the Electronic diary before Week 6 divided by the number of participants who reported new or increased symptoms in the Electronic Diary before Week 6, reported as a percentage.
- c. Number of participants who administered self-swab #2 and reported new or increased symptoms in the Electronic diary before Week 6 divided by the number of participants who administered self-swab #2 before Week 6, reported as a percentage.

6.2.4.3. Percentage of self-swabs with valid (positive or negative) or invalid (non-reportable due to technical or self-collection failures) results

- a. Number of self-swabs #1 with **valid (positive or negative) result** for each of SARS-CoV-2/Flu A/Flu B/RSV divided by total number of self-swabs #1 received, reported as percentages.
- b. Number of self-swabs #2 with **valid (positive or negative) result** for each of SARS-CoV-2/Flu A/Flu B/RSV divided by total number of self-swabs #2 received, reported as a percentage.
- c. Total number of self-swabs (#1 and #2) with **valid (positive or negative) result** for each of SARS-CoV-2/Flu A/Flu B/RSV divided by total number of self-swabs (#1 and #2) received, reported as a percentage.
- d. Total number of self-swabs (#1 and #2) with **NOT DONE** divided by total number of self-swabs (#1 and #2) reported in the Electronic diary (Record Swab), reported as a percentage.

CCI [REDACTED]

[REDACTED]

[REDACTED]

[REDACTED]

[REDACTED]

[REDACTED]

[REDACTED]

[REDACTED]

[REDACTED]

[REDACTED]	[REDACTED]
------------	------------

CCI [REDACTED]	[REDACTED]
[REDACTED]	[REDACTED]
[REDACTED]	[REDACTED]

[REDACTED]

[REDACTED]

[REDACTED]

[REDACTED]

[REDACTED]

[REDACTED]

[REDACTED]

[REDACTED]

[REDACTED]

CCI [REDACTED]

[REDACTED]

[REDACTED]

[REDACTED]

[REDACTED]

[REDACTED]

[REDACTED]

[REDACTED]

[REDACTED]

[REDACTED]

[REDACTED]

[REDACTED]

[REDACTED]

[REDACTED]

[REDACTED]

[REDACTED]

6.4. Subset Analyses

The study participants and analysis sets may be split in three acute viral respiratory illness groups (SARS-CoV-2, Influenza virus, and RSV) and the primary analysis detailed in [Section 6.1.1](#) may be conducted on each group separately, if the n for each of the groups is deemed sufficient. Summary plot of well-to-sick changes by day in symptomatic positive participants may also be generated in four gender/age sub-groups (Male >60 y/o; Male <=60 y/o; Female >50 y/o; Female <=50 y/o) for each of the symptoms and statistically significant voice features (based on primary analysis) if data allows.

6.5. Baseline and Other Summaries and Analyses

6.5.1. Baseline Summaries

Demographic data and specific components of the enrollment questionnaire as listed in [Section 3.4](#) will be summarized, and their descriptive statistics (n / percentages and/or mean, median, maximum and minimum statistics as appropriate) summarized and tabulated.

6.5.2. Study Conduct and Participant Disposition

Participants' evaluation, disposition and discontinuation will be summarized according to Pfizer standards.

6.5.3. Study Treatment Exposure

N/A.

6.5.4. Concomitant Medications and Nondrug Treatments

N/A.

6.6. Safety Summaries and Analyses

The safety analysis set is the FAS. The incidence and severity of adverse events (AEs)/research related injuries (RRIs) will be summarized according to Pfizer standards.

7. INTERIM ANALYSES

7.1. Introduction

An interim analysis (IA) #1 will be conducted once the first 1000 participants have completed the study to reassess study feasibility and enrollment requirements, including sample size.

An additional IA #2 may be conducted to evaluate the study primary and secondary objectives, and the algorithm development analyses detailed in the appendix SAP based on Cohort 1 data, consisting of approximately 9,100 participants who have been enrolled by 15 Feb 2022, prior to protocol amendment #2.

7.2. Interim Analyses and Summaries

7.2.1. IA #1

The list of study feasibility and compliance measures that will be summarized for the IA is:

- Number of participants enrolled
- Number of participants completed
- Number of participants without symptoms at enrollment (including or excluding chronic symptoms)
- Self-swab #1, number completed and by its outcome

- Self-swab #2, number completed before and after Day 42, and by its SARS-CoV-2 outcome (if after Day 42, number symptomatic participants during Day 42 – Day 56)
- Average % day Electronic diary completion, and before or after self-swab #2
- Average % quality voice Electronic diary entries
- Number of well to symptomatic sick (SARS-CoV-2) participants

All 1000 participants (the IA analysis set) will be included in the interim analysis based on observed cases, and missing data will not be imputed. To define the well to symptomatic sick participants for the IA, all following conditions need to be met to be included:

- Without symptoms at enrollment (two participant sets will be considered: including or excluding chronic symptoms)
- Negative self-swab #1 results for SARS-CoV-2, Influenza, and RSV
- Positive self-swab #2 result for SARS-CoV-2
- Reported new or increased symptoms during the study

Number and its percentage, or median/minimum/maximum will be summarized as appropriate. The summary will be produced for all participants, as well as by gender/age groups (i.e. Male >60 y/o; Male <=60 y/o; Female >50 y/o; Female <=50 y/o).

In addition, for the IA analysis set as well as for the well to symptomatic sick SARS-CoV-2 participant sets (including or excluding chronic symptoms at enrollment), the number of participants with quality Electronic diary completion will be plotted along day for all participants, and by gender/age groups.

7.2.2. IA #2

The analyses and summaries for this IA will include the primary and secondary analyses detailed in [Section 6.1](#) and [Section 6.2](#) respectively, and the algorithm development analyses detailed in appendix SAP ([Section 8 Appendix A](#)).

8. APPENDICES**Appendix A. X9001293 Algorithm Development Statistical Analysis Plan****Appendix B. List of Abbreviations**

Abbreviation	Term
AcRIS	acute respiratory illness surveillance
ADAM	adaptive moment estimation
AE	adverse event
AR	autoregressive
AUC	area under the curve
AWS	amazon web services
CI	confidence interval
CNN	convolutional neural network
dB	decibel
EOS	end of study
FAS	full analysis set
FFT	fast Fourier transform
FN	false negatives
FP	false positives
IA	interim analysis
LGBM	light gradient boosting machine
CCI	
MFCC	mel frequency cepstral coefficients
MMRM	mixed-effects model with repeated measures
N/A	not applicable
PCA	principal component analysis
PPS	predictive power score
RNN	recurrent neural networks
ResNET	residual neural network
RFECV	recursive feature elimination with cross validation
ROC	receiver operating characteristics
RRIs	research related injuries
RT-PCR	reverse transcription polymerase chain reaction
RSV	respiratory syncytial virus
SAE	serious adverse event
SAP	statistical analysis plan
SARS-CoV-2	severe acute respiratory syndrome coronavirus 2
SD	standard deviation
SGD	stochastic gradient descent
SHAP	shapley additive explanations
SNR	signal-to-noise ratio
SVM	support vector machine
STFT	short-time Fourier transform
TN	true negatives

Abbreviation	Term
TP	true positives
t-SNE	t-distributed stochastic neighbor embedding
UMAP	uniform manifold approximation and projection
CCI	[REDACTED]
VGG	visual geometry group
WAV	waveform audio file format
XGBoost	extreme gradient boosting
y/o	years old

Protocol X9001293

**Acute Respiratory Illness Surveillance (AcRIS) by Monitoring Voice and Illness
Symptom Changes using a Mobile application in a Low-Interventional Decentralized
Study**

**Algorithm Development Statistical Analysis Plan
(adSAP)**

TABLE OF CONTENTS

LIST OF TABLES 4

LIST OF FIGURES 4

1. INTRODUCTION 5

2. DEFINITIONS AND CONVENTIONS..... 5

3. ANALYSIS SETS (POPULATIONS FOR ANALYSIS)..... 5

4. GENERAL METHODOLOGY AND CONVENTIONS..... 7

 4.1. Hypotheses and Decision Rules 7

 4.2. General Methods 8

 4.2.1. Voice Data Preparation..... 8

 4.2.2. Voice Feature Extraction 8

 4.2.3. Feature Selection and Dimensionality Reduction Methods..... 9

1. INTRODUCTION

This Appendix to the X9001293 SAP provides the detailed methodology for summary and statistical analyses related to the development of the screening algorithm for Symptomatic COVID-19 illness using voice features and symptoms data collected in the X9001293 study.

2. DEFINITIONS AND CONVENTIONS

The longitudinal nature of the data collected in X9001293 study (i.e., well and sick state data from the same participants) allows for a robust estimation of well and sick states and provides a controlled dataset for the training of the algorithm.

Definition of Total Symptom Score: the sum of all the symptom responses in the Electronic Diary converted to a numeric as described in Section 5.2.2.1. of the main SAP.

3. ANALYSIS SETS (POPULATIONS FOR ANALYSIS)

Data for all participants will be assessed to determine if participants meet the criteria for inclusion in each analysis population prior to releasing the database and classifications will be documented per standard operating procedures.

Algorithm Population	Description
Full Analysis Set (FAS) as per the Main SAP	All participants who sign the informed consent document and enroll in the study, as defined in the main SAP. Qualified participants are males or females aged 18 years and older (or the minimum state-specific age of consent if > 18) at Screening visit, who are willing and able to comply with daily symptom and voice assessments on the Electronic Diary application and other study procedures including self-collection of nasal swabs, are expected to be available for the duration of the study, and are capable of giving informed consent.
Primary Analysis Set	Participants in FAS who have a negative RT-PCR test (at swab #1) and no acute symptoms (as determined by the enrollment questionnaire), and who become positive for SARS-CoV-2, influenza virus, or RSV (at swab #2) and symptomatic during the study.
Secondary Analysis Set A	Participants in FAS who have a negative RT-PCR test (at swab #1) and a negative RT-PCR test (at swab #2) irrespective of symptoms.
Secondary Analysis Set B	Participants in FAS who have a positive SARS-CoV-2, influenza virus, or RSV RT-PCR test (at swab #1) and are symptomatic.
CCI [REDACTED]	[REDACTED]

For the purpose of algorithm development and testing, the sick and well states are defined for each of the analysis sets (when applicable).

For Primary Analysis Set

The **sick state** is defined by considering a window of Electronic Diary data around a positive RT-PCR test at swab #2.

To determine the start of the sick state window, consider the difference in symptoms between consecutive recordings. The start of the sick window will be a symptom increase within 3 days prior to swab 2. If there is no symptom increase within these 3 days, the start of the window will be on swab #2 day.

If the number of days between swab #1 and swab #2 is less than or equal to 3, the sick state window will start on swab #2 day.

The *end of the window* is after swab #2 and defined by either:

- a. The last time the total symptom score is above 40% of the maximum total symptom score, or
- b. The final available datapoint if the total symptom score stays above 40% of the maximum score.

If the total symptom remains below 40% of the maximum total symptom score after swab #2, the end of the window will be the swab #2 day.

The **well state** is defined by considering a window of Electronic Diary data around a negative RT-PCR test at swab #1, from 8 days before swab #1 up to 14 days before a positive swab #2. If there are less than 14 days between swab #1 and swab #2, the well state window ends on the day of swab #1.

For Secondary Analysis Set A

The **well state** is defined by considering an:

- Analysis time window from 8 days before swab #1 up to 8 days after swab #1.
- Analysis time window of 8 days up to and including swab #2.

For Secondary Analysis Set B

The **sick state** is defined by considering an analysis time window of 3 days before and 3 days after swab #1, including swab #1 day.

CCI

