5.2.2.5. Correlation Between Symptoms and Voice Features

Change from baseline in symptom, after first occurrence of new or increased symptoms and before return to well state based on Electronic diary, will be modelled using a mixed-effects model with repeated measures (MMRM) with the change from baseline in the voice feature as covariate, day (categorical factor) as fixed effect, and participant as random effect. For the purpose of this analysis, the baseline is defined as the average of the endpoint values during the period up to 7 days before the first occurrence of new or increased symptoms, and the first occurrence of new or increased symptoms at day = 1. The day of return to well state is defined as the first day after the Maximal Score Day (defined in [Section 5.2.2.2](#)) when the total symptom score is less than or equal to the Initial Symptom Score (defined in [Section 5.2.2.1](#)).

Autoregressive AR(1) variance-covariance structure will be used for the MMRM. The estimate of the coefficient for the change in voice feature, its standard error, 90% CI, and p-value will be presented.

Pearson and Spearman rank order correlations between changes in symptoms and voice features will also be computed for each participant across days. These correlations will be summarized across participants. A heatmap plot will also be presented for each of these correlations.

CCI

CCI [REDACTED]

[REDACTED]

[REDACTED]

[REDACTED]

[REDACTED]

[REDACTED]

[REDACTED]

[REDACTED]

[REDACTED]

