5.2.3. Analyses for Categorical Endpoints

For Electronic diary symptom measures that have ordinal categorical responses, the values will be converted to numeric values (i.e. 0-4 for fever and 0-7 for other symptoms, where 0 = no symptoms), and analyzed as continuous endpoints according to [Section 5.2.2](#).

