6.1.1. Main Analysis

6.1.1.1. Well to Sick

- Estimator: Primary Estimator E1(Section 2.1.1). This estimator is intended to provide a population level estimate of the well state as well as changes in symptoms and voice features from well to sick in symptomatic SARS-CoV-2, influenza virus, or RSV positive participants using Electronic diary.
- Analysis Sets: (a) Participants in Primary Analysis Set (Section 4) who become SARS-CoV-2, influenza virus or RSV positive (at Swab#2) and symptomatic during the study; (b) A subset of (a) who are symptom free at enrollment; (c) A subset of (a) who have symptoms due to chronic pre-existing conditions at enrollment. These analysis sets will be considered as deemed appropriate by data.
- Intercurrent events and missing data: (a) There are no particular intercurrent events considered. Participants who have events that lead to missing data will be included and missing data will not be imputed. (b) Inadequate compliance – data will be used as recorded.
- Statistical Method: Summary statistics and linear mixed effect analyses as described in Section 5.2.2.3. The total symptom score, each symptom and each voice feature will be modelled individually.
- Summaries:
 - a. Descriptive summaries and corresponding plots of the mean/SD will be provided. For linear mixed effect model analyses, estimates for all parameters fixed effect means, standard errors, 90% CIs, and p-values, as well as the variance estimates for their

random effects will be provided (as described in [Section 5.2.2.3](#)). Results from all models will be presented in a table.

- b. To assess the well-to-sick analysis baseline: For voice features that are determined as statistically significant based on linear model mixed effect analysis, the difference of the voice feature values between every pre-symptomatic day (starting from enrollment day) and the well-to-sick baseline (i.e. 7-day average before symptomatic onset as described in [Section 5.2.2.3](#)) will be computed. The mean/SD of the differences across participants in the analysis set will be plotted by day up to the symptomatic onset.

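### The 40%-of-maximum end of the appendix's sick window can label recovered days as sick, in participants with chronic symptoms and in mild cases with one later stray symptom

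*SAP*

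**What the plan says.** adSAP Section 3 labels diary days for the Primary Analysis Set as follows.

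- **Start of sick window:** "The start of the sick window will be a symptom increase within 3 days prior to swab 2"; without such an increase, the day of swab #2.
- **End of sick window:** "The last time the total symptom score is above 40% of the maximum total symptom score", or "The final available datapoint if the total symptom score stays above 40% of the maximum score". The fallback that closes the window on swab #2 day applies only under this condition: "If the total symptom remains below 40% of the maximum total symptom score after swab #2".
- **Score:** adSAP Section 2 defines it as "the sum of all the symptom responses in the Electronic Diary converted to a numeric". SAP 5.2.3 gives the item scale as "0-4 for fever and 0-7 for other symptoms, where 0 = no symptoms".
- **Well window:** from 8 days before swab #1 to 14 days before the positive swab #2. It ends on swab #1 day if the swabs are less than 14 days apart.

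The end rule has no baseline adjustment, no consecutive-day requirement and no cap on length. The period over which the maximum is taken is not stated.

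The Primary Analysis Set excludes only acute symptoms at enrollment. SAP 6.1.1.1 expects chronic symptoms among the cases and names "A subset of (a) who have symptoms due to chronic pre-existing conditions at enrollment". Participants with a positive swab keep the diary to the end of Week 8 (Protocol 8.1.2).

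The main SAP has a different, baseline-referenced rule in 5.2.2.5. "The day of return to well state is defined as the first day after the Maximal Score Day" on which the total is no higher than the Initial Symptom Score, which is the highest total over the first three days with data (5.2.2.1). The appendix does not use it.

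**The concern.** A threshold set as a fraction of a raw maximum does not separate illness from a participant's ordinary level. A participant who returns fully to a chronic level above the threshold never leaves the sick window, and the same score before infection, inside the well window, carries the opposite label.

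Because the rule looks for the last exceedance and not the first return, a single unrelated symptom weeks later can also reopen a window, and every day in between becomes sick.

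These labels train and test the classical models (adSAP 5.1), the deep learning models (5.2) and the change-from-baseline models (5.4). Analysis 5.4 does not escape, because adSAP 4.5 subtracts the baseline from the endpoint values and not from the score that sets the window. Recovered days in the sick class blur the voice contrast and can distort the observed sensitivity, for which adSAP 4.1 sets a success criterion of 70%.

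**Working it through.** The plan states no window length or mislabelling rate, so there is no figure of its own to reproduce. The check applies the written rule directly.

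**Inputs from the documents.** Threshold 40% of the maximum M (adSAP 3). Diary to Day 56 for positive participants (Protocol 1.3, 8.1.2). 16 diary symptoms (Protocol 8.1.1), so the largest possible total is 4 + 15 × 7 = 109.

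**Assumptions.** All score levels, illness lengths and day-to-day variation below are assumed; the documents give none.

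**1. Chronic level.** Let the constant usual score be B and the illness rise I, so M = B + I. The window stays open after recovery when B > 0.4(B + I), that is, when I < 1.5B.

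| B | Largest whole-number M with the window open to the end |
|---|---|
| 4 | 9 |
| 6 | 14 |
| 10 | 24 |

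For B = 6 and M = 14: 0.4 × 14 = 5.6, and 6 > 5.6. For B = 6 and M = 16: 0.4 × 16 = 6.4, so no recovered day is labelled sick. For B = 4 and M = 20: 0.4 × 20 = 8, again none.

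**2. Days involved.** Take B = 6, M = 14 and a 10-day illness starting two days before swab #2. The first day back at 6 is swab day + 8, so the recovered days labelled sick number 56 − (swab day + 8) + 1 = 49 − swab day.

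| Swab #2 on Day | 10 | 14 | 21 | 28 | 35 |
|---|---|---|---|---|---|
| Recovered days labelled sick | 39 | 35 | 28 | 21 | 14 |

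For swab #2 on Day 21 the window is Days 19 to 56, which is 38 days, and 28 of them (28/38 = 74%) come after the return to the usual score. The main SAP's own rule puts return to well on Day 29.

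**3. Fluctuating chronic level.** Daily scores were simulated as Poisson around the usual level (swab #2 on Day 21, 10-day illness, 4,000 participants per setting). The table gives the probability of at least 14 recovered days labelled sick.

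| Usual mean | I = 8 | I = 12 | I = 16 | I = 24 |
|---|---|---|---|---|
| 6 | 1.00 | 0.95 | 0.78 | 0.18 |
| 3 | 0.88 | 0.46 | 0.14 | 0.00 |

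Fluctuation widens the condition in step 1, because one high day late in the diary is enough. A large rise on a low usual level remains unaffected.

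**4. Stray symptom, usual score 0.** A later score s reopens the window when s > 0.4M, that is, when M < 2.5s.

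| s | 1 | 2 | 3 | 4 | 5 |
|---|---|---|---|---|---|
| Largest M affected | 2 | 4 | 7 | 9 | 12 |

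Example: M = 7, swab #2 on Day 21, back at 0 from Day 26, one score of 3 on Day 50. Since 3 > 2.8, the end moves from Day 24 to Day 50, and 50 − 26 + 1 = 25 recovered days are labelled sick.

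**5. Possible effect on the success criterion.** Suppose sensitivity is scored per session, a fraction f of sick-labelled sessions are recovered days, and these are called sick 40% of the time (one minus the 60% target specificity). Observed sensitivity is then S(1 − f) + 0.4f. A true S of 0.80 falls to 0.70 at f = (0.80 − 0.70)/(0.80 − 0.40) = 0.25. A true S of 0.75 does so at f = 0.05/0.35 = 0.14.

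**The case against.** **The plan has analyses free of the long tail.** A reader might infer that every model is affected. The documents do not support that. adSAP 4.4/5.3 uses 3 days either side of the maximum score, and Secondary Analysis Set B uses 3 days either side of swab #1. This limits the scope but does not remove the point: 4.4 is additional to 5.1 and 5.2, and the models tested on Set B under 5.5.2 include those trained on Section 3 labels.

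**The effect is conditional.** A reader might infer that participants with chronic symptoms generally have weeks of mislabelled days. They can have them; whether they do depends on the ratio of usual to maximum score. A simulation with usual/maximum scores of 4/8, 5/10, 6/14 and 9/20 sends 100% of windows to the last day, but those ratios (50%, 50%, 43%, 45%) all exceed 40%, so the result is built in. The maxima are also small against a possible 109. This stands in full.

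**The stray-symptom case is narrower.** With a usual score of 0, a maximum of 3 to 4 and stray scores of 1 to 2 on 5% of days, about half of windows were extended, but the median extension was 0 days and 28–29% of participants gained 14 days or more. This also stands. One could further read the end rule as the end of the first unbroken run above the threshold, which would remove this case. The text does not say so, and a constant chronic level above the threshold would still run to the final datapoint.

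**No loss of sensitivity is shown.** Step 5 rests on per-session scoring and an assumed classifier, whereas adSAP 4.1 counts 100 participants as cases. It shows what could happen and is not an estimate.

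**Conclusion.** The concern holds as a defect in a stated rule. Under adSAP Section 3, recovered days can be labelled sick up to the last diary day whenever a constant usual score exceeds 40% of the maximum, while the same score inside the well window is labelled well. With a usual score of 0, one later symptom of score s does the same up to its own day when the maximum is below 2.5s. It reaches the models in adSAP 5.1, 5.2 and 5.4.

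The mechanism follows from the text and simple arithmetic, so confidence in it is high. The impact is unknown: the documents give neither score distributions nor the frequency of chronic symptoms, and the simulations only illustrate the mechanism. No claim can be made about how many participants are affected, or how far observed sensitivity would move. The rule should be changed before the labels are used.

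**What to change.** End the sick window at the earlier of:

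1. the current end; and
2. the day before the first two consecutive recorded days after swab #2 with total score at or below the participant's Initial Symptom Score (SAP 5.2.2.1, the same level as the return to well in 5.2.2.5).

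Compute the maximum for the 40% rule only from the window start up to that return. If no such return is recorded, the current end stands. Keep the present rule as a sensitivity analysis.

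In the step 2 example with swab #2 on Day 21, Days 29 and 30 are the first two at 6, so the window ends on Day 28 with no recovered days. In the step 4 example it ends on Day 25. Applying 40% to the rise above baseline would instead end the step 2 window on Day 25, dropping Days 26 to 28, when the score is still above its usual level.

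**Cost:** one rule in the appendix and a re-run of labelling and of the models that use it; no new data. There will be fewer sick-labelled days per participant, and a relapse after two well days would be cut off. The Initial Symptom Score rests on three days, so where it is unusually low a return may never be recorded and the long window remains.

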- b. Participant is required to perform self-swab #2 if they develop new or increased symptoms.
- c. Participant is required to perform self-swab #2 if they have remained asymptomatic at day 42+1.
- d. Participant is required to record End of Study Questionnaire at Day 42 +4 days (for participants who have tested negative or invalid for both self-swab #1 and #2).
- e. Participant is required to record End of Study Questionnaire at Day 56 (for participants who have had a positive result for either self-swab #1 or #2)
- f. Participant is deemed positive for virus if biological sample is determined to contain SARS-CoV-2 and/or influenza virus and/or RSV viruses as detected by RT-PCR test.

Please note for the table when the two numbers for a day are separated by a "+", what it means is that the swab may be taken as soon as the first number of the two and as late as the sum of the first and second of the numbers.

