6. ANALYSES AND SUMMARIES

Throughout the analyses, a participant is defined as symptomatic if they report at least one new or increased symptom in the Electronic diary during the course of the study.

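### The algorithm's well window for cases has no symptom condition, so a swab #2 taken 14 or more days after onset puts the first days of that illness in the well class

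*SAP*

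**What the plan says.** **Well window.** For the algorithm's cases, adSAP Section 3 places the well window "around a negative RT-PCR test at swab #1, from 8 days before swab #1 up to 14 days before a positive swab #2". A second clause covers swabs taken close together: "If there are less than 14 days between swab #1 and swab #2, the well state window ends on the day of swab #1". Both are date rules only.

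**Sick window.** It is anchored on swab #2. It can open up to 3 days earlier if symptoms rose in that time; otherwise, "If there is no symptom increase within these 3 days, the start of the window will be on swab #2 day". If the total score stays below 40% of its maximum after swab #2, "the end of the window will be the swab #2 day".

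**Entry to the set.** Participants start with a negative swab #1 and no acute symptoms on the enrolment questionnaire, then "become positive for SARS-CoV-2, influenza virus, or RSV (at swab #2) and symptomatic during the study". Main SAP Section 6 counts a participant as symptomatic on a study-wide basis: "defined as symptomatic if they report at least one new or increased symptom in the Electronic diary during the course of the study".

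**Timing of swab #2.** The Schedule of Activities (Protocol 1.3) lists the symptomatic swab #2 as Day 2 + 40 days, and its note explains that "the swab may be taken as soon as the first number of the two and as late as the sum" of the two numbers. That is Day 2 to Day 42. No limit is counted from onset. Main SAP 6.2.4.2 summarises the onset-to-swab delay but does not use it to select participants.

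**Main SAP.** Section 5.2.2.4 closes the well state on the last day before onset, and 5.2.2.1 derives the onset date from the diary.

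**The concern.** These labels are the truth against which the classifiers are trained and scored. The classical and deep-learning analyses (adSAP 5.1 and 5.2) use the set whose windows Section 3 defines, and the change-from-baseline analysis (4.5) reuses those windows explicitly.

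A case who swabs late can have voice recordings from the acute illness entered as well. If that person has recovered by the swab, a recovered recording is entered as sick. The classifier then learns from reversed labels, and hold-out specificity and sensitivity partly reflect how promptly people swabbed. Section 4.1 sets a success criterion of 70% observed sensitivity and a minimum target of 60% specificity.

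The two parts of the SAP also disagree: the same diary day can lie after onset, and so outside the well state, in the primary analysis, yet count as well for the algorithm.

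**Working it through.** The plan states no figure for mislabelled days, so there is none to reproduce. The check applies the Section 3 rules to dated examples.

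**Inputs from the documents:** the window rules (adSAP 3) and a symptomatic swab #2 on any day up to Day 42 (Protocol 1.3).

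**Assumed:** onset on day O, after a negative swab #1; illness on L consecutive days; swab #2 on day O + D, detecting that illness.

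**1. Illness days labelled well.** With D ≥ 14 and onset after swab #1, the swabs are more than 14 days apart, so the close-swab clause does not apply. The last well day is O + D − 14. The illness occupies O to O + L − 1. The overlap is (O + D − 14) − O + 1 = D − 13 days, and at most L.

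Example: swab #1 on Day 4, onset on Day 8, L = 10 (illness Days 8–17).

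| D | swab #2 | well window | illness days labelled well |
|---|---|---|---|
| 14 | Day 22 | Days 1–8 | 1 |
| 16 | Day 24 | Days 1–10 | 3 |
| 21 | Day 29 | Days 1–15 | 8 |
| 23 | Day 31 | Days 1–17 | 10 (all) |

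A 7-day illness is wholly inside from D = 20. Below D = 14 no day of such an illness is labelled well.

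**2. Sick window in the same cases.** The further assumptions are a symptom peak two days after onset, no rise in the 3 days before swab #2, and the 40% rule read against the maximum over the whole study (the adSAP does not state the period). For illnesses of 7 to 14 days and delays of 14 to 28 days, the sick window is the swab #2 day alone, with a score of zero. For a 21-day illness, that single day still carries low residual symptoms at D = 14 to 18; by D = 21 it is a recovered day.

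**3. Effect on measured specificity.** Assume 20 hold-out cases (20% of the planned 100, using the example split in adSAP 4.2.5.1), 13 well days each, true specificity 80% and true sensitivity 70%. An ill day labelled well is scored correct with probability 1 − 0.70 = 0.30 instead of 0.80, a shift of 0.50. Well days number 20 × 13 = 260. Loss from one case:

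- D = 14: 1/260 × 0.50 = 0.2 points
- D = 16: 3/260 × 0.50 = 0.6 points
- D = 21: 8/260 × 0.50 = 1.5 points
- D ≥ 23, L = 10: 10/260 × 0.50 = 1.9 points

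**4. After the change.** Ending the window at min(swab #2 − 14, O − 1) brings illness days labelled well to 0 at every delay.

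**5. The plan's alternative windows (adSAP 4.4).** In the same example the maximum falls on Day 10, 6 days after swab #1. The well window therefore ends on Day 4 and the sick window is Days 7–13. No illness day is labelled well, and the peak is labelled sick.

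**The case against.** The strongest reply is that the protocol does not plan for late swabs. Protocol 1.3 and 8.1.2 require swab #2 when symptoms develop, 8.1.3 adds a daily reminder, and 4.2.1 has staff follow up noncompliance. The Day 2 to Day 42 span exists because onset can fall on any date. A long delay also matters only if RT-PCR is still positive then, on which the documents are silent. A long gap may instead reflect an earlier, unrelated symptom rise followed by a later infection; those well-labelled days would be symptomatic but not the confirmed illness. All of this stands. It limits how often the problem occurs but does not remove it from the rule.

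Section 4.4 largely avoids the problem. But it is an additional analysis, adSAP 5.3 makes it conditional on the data, and it leaves the Section 3 labels unchanged.

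Four stronger readings are tempting but unsupported:

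- A reader might infer that any delay beyond two weeks places the whole illness in the well class. Just past 14 days it is only the first day or so. Acute days left in neither class at shorter delays are unused, not mislabelled.
- A reader might infer that one late case costs 5 points of sensitivity (1 of 20). adSAP 4.2.5.2 and 4.2.5.3 point to counting by prediction, not by participant. If the other 19 hold-out cases had 6 sick days each (an assumption), one recovered sick day would cost at most 1/(19 × 6 + 1) = 0.9 points.
- A reader might infer that symptomatic days before a negative swab #1 are also mislabelled target illness. By the plan's own reference test they are not shown to be.
- A reader might infer that every symptomatic day should leave the well class. That would strip non-target symptoms from the negatives and could flatter specificity for a general-population screen.

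**Conclusion.** The point holds as a gap in the labelling rule and a conflict with main SAP 5.2.2.4. When swab #2 follows onset of the detected illness by D ≥ 14 days, min(L, D − 13) illness days are labelled well. If symptoms have resolved without a late rise, the sick class receives only the swab #2 day.

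The number of affected cases is unknown and may be small or nil, because the documents give no distribution of the delay. Under the stated assumptions each affected hold-out case lowers measured specificity by about 0.2 to 2 points; the upper part of that range needs a delay of about three weeks or more. The effect on model training is not quantified.

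A reader might also infer that the rule could produce a false success. The scoring errors described here lower measured performance, so the documents do not support that. The rule should be corrected because the labels underlie the main algorithm analyses and the change is cheap, not because the results are shown to be badly distorted.

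**What to change.** In adSAP Section 3, end the well window for Primary Analysis Set cases at the earlier of (a) 14 days before swab #2 and (b) the day before onset as derived in main SAP 5.2.2.1. When the swabs are less than 14 days apart, end it at the earlier of swab #1 day and the day before that onset. Report how many cases have an onset-to-swab #2 delay of 14 days or more, and repeat the performance measures without them as a sensitivity analysis.

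The cost is SAP wording and one date that the main SAP already derives from the diary. The drawback is fewer well days for some cases, including anyone with an early, unrelated symptom rise, because 5.2.2.1 takes the first rise in the study and the documents do not define the episode that led to swab #2. That is also why late-swab cases are better set aside in a sensitivity analysis than dropped from training and hold-out. The change does not alter the sick window; the sensitivity analysis shows how much the single-day sick labels of these late cases matter.
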